5.4 Preparation and Administration of Study Drug

The study medications will be stored, packaged and dispensed from the UIC Eye and Ear Infirmary (EEI) Pharmacy. The study medications will be dispensed in sterile eye droppers of 3 ml volume (each containing 400- 500µl of the study medications), which will be used as single-dose applications. One drop of the drug/ placebo solution will be administered to each eye. Therefore 4 eyedroppers will be required per day. At each visits, subjects will receive 56 sterile multi-dose eye droppers that will be used as single-dose applications. Prepared eye droppers will be placed in a dark (brown) colored zip-lock packet before being dispensed to the subject. The medications will need to be stored in a refrigerator (4 °C), away from direct strong light.

Instructions for Drug Use:

1. Wash your hands thoroughly with soap and water.
2. Check the dropper tip to make sure that it is not chipped or cracked.
3. Avoid touching the dropper tip against your eye or anything else – eye drops and droppers must be kept clean.
4. While tilting your head back, pull down the lower lid of your eye with your index finger to form a pocket.
5. Hold the dropper (tip down) with the other hand, as close to the eye as possible without touching it.
6. While looking up, gently squeeze the dropper so that a single drop falls into the pocket made by the lower eyelid. Remove your index finger from the lower eyelid.
7. Close your eye for 2 to 3 minutes and tip your head down as though looking at the floor. Try not to blink or squeeze your eyelids.
8. Place a finger on the tear duct and apply gentle pressure.
9. If you are to use more than one drop in the same eye, wait at least 5 minutes before instilling the next drop.
10. Do not reuse the dropper after use. Use another dropper for next dose.

The subject should repeat the above procedures for the other eye to demonstrate to the Investigator or designee that they are able to perform the drug administration satisfactorily.

Subjects will be instructed to perform these steps on each administration of the study medication.

Instructions for use will be included in the zip-lock packet with the study medication and site personnel will ensure that these instructions are given to the patient.

5.5 Subject Compliance Monitoring

Subjects will receive their first dose of study medication on study Day 1 in the doctor's office and after completion of the study assessments will have the topical eye drops dispensed for self-administration.

Subjects will be provided with diaries to record the time of each dose and will also be asked to record any adverse symptoms. In addition, they will be asked to make a note of any missed doses together with the reason for the omission. Subjects will be asked to bring their diaries with them at the 2, 4, 6 and 8 week visits. Diaries will be reviewed with the subject by a member of the research team at each visit. Additionally, subjects will be asked to bring back the used and unused drug eye droppers at each study visit. Participants will be asked to return the unused eye droppers each study visit as a method to determine compliance.

5.6 Prior and Concomitant Therapy

Prior medications are defined as all medications taken within 30 days prior to Day 1, whether there is continued use or not. Concomitant medications must be identified in the patient's medical record, including all lubricants administered for Dry Eye Disease. These medications will be recorded in the case report form (CRF).

• For each medication taken, the following information will be collected:

1. Medication trade name
2. Eye that was treated, if applicable
3. Indication for which the medication was given

4. Date started
5. Date stopped
6. Dose of medication used.

There will be a 2-week washout period of topical corticosteroids and topical cyclosporine before enrollment and these medications are prohibited throughout the study. Other than these, participants will be permitted to continue their chronic DED treatments which include the use of artificial tears, eyelid massage, or warm compresses. The number of drops and frequency must be recorded in the patient diary provided.

- The use of any investigational agent during past 30 days is prohibited.

There is only one FDA approved treatment currently available to treat patients with Keratoconjunctivitis Sicca (dry eye disease)- Cyclosporine 0.05% (marketed as Restasis). The FDA approved indication for Restasis use is the following: “to increase tear production in patients whose tear production is presumed to be suppressed due to ocular inflammation associated with keratoconjunctivitis sicca”. Restasis will be withheld during the course of this study. This is necessary as the proposed mechanism of action of rhDNase in dry eyes is to reduce inflammation on the surface of the eye. Restasis can also reduce inflammation albeit via a different mechanism. Thus, because of over lapping anti-inflammatory actions, it may not be possible to attribute any observed clinical benefit to rhDNase treatment if Restasis is used concurrently. This approach has been used in other clinical trials that have investigated the use of an anti-inflammatory agent in dry eye disease.³²

It is ethical to withhold Restasis because, as its FDA approved indication suggests, the clinical benefit of using Restasis is increased production of tears. While receiving DNase1, patients will continue to receive artificial tears as needed. Therefore, although the patients may not have an increase in tear production if Restasis is withheld, the ocular surface will receive sufficient lubrication and hydration due to the use of artificial tears.

Holding Restasis may increase the risk of worsening of DED during the wash-out period and during the course of the study. However, because artificial tears will be used during the wash out period as well as during the course of the study as needed, we do not expect any significant clinical worsening during the study. We do however expect the frequency of use of artificial tears to go up during the wash out period and during the course of the study.

The subjects will be monitored frequently (at 2 weekly intervals) to ensure that they are not subjected to any undue risks during the wash out period or during the course of the study. Additionally, they will be warned of the possible signs and symptoms of clinical worsening of DED, and advised to contact the research team immediately in case any of those symptoms occur. Subjects will also be encouraged to contact the research team in case they experience any ocular discomfort during the wash out period or during the course of the study. The subject's condition will be monitored by the physician (Principal Investigator) at each study visit, as well as at any interim visit (in case of adverse symptoms, as mentioned above). Any worsening of DED or any adverse event due to the study drug will be recorded. In case of clinical worsening, based on the individual subject's clinical condition, one or more of the following therapeutic decisions may be implemented: (1) Increasing the frequency of use of artificial tears, (2) Re-starting the use of anti-inflammatory therapy (Restasis/ corticosteroids), (3) Withdrawal of the use of study drug (if worsening occurs during the course of the study). The decision will be made by the physician (Principal Investigator) based his clinical judgment as per the individual subject's clinical condition. If additional anti-inflammatory therapy (Restasis/ corticosteroids) is instituted during the wash-out period, the subject will be excluded from the study. Also, if additional anti-inflammatory therapy (Restasis/ corticosteroids) is instituted during the course of the study and/or the study drug is

withdrawn, the subject will be excluded from the study. After any clinical worsening is noted, the subjects will be followed more closely (weekly) until complete resolution of symptoms and return to the subject's previous baseline.

5.7 Rescue Plan

The research staff, including the PI, will be masked to randomization, thus will not be aware if a particular subject receives study drug or placebo. Subjects will be monitored by the Principal Investigator at each study visit. Any worsening of DED or any adverse event (AEs) will be recorded and in the case of AEs followed to resolution. In case of clinical worsening/ adverse event(s), based on the individual subject's clinical condition, one or more of the following therapeutic decisions may be implemented:

- (1) Increasing the frequency of artificial tears use,
- (2) Re-starting the use of anti-inflammatory therapy (Restasis/ corticosteroids),
- (3) Discontinue the study drug.

The decision will be made by the Principal Investigator based on his clinical judgment and the individual subject's clinical condition. If additional anti-inflammatory therapy (Restasis/ corticosteroids) is instituted and/or the study drug is discontinued, the subject will be withdrawn from the study. If an adverse event is severe enough to discontinue the subject from the study, the PI may decide to break the subject's randomization code if it seems relevant to the treatment of his/her ocular condition at that time. He/ She will receive the treatment required for his/ her eye condition as per established clinical guidelines.

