6.5.3	Visit 3: Week 2 (\pm 2 days)	25
6.5.4	Visit 4: Week 4 (\pm 2 days)	25
6.5.5	Visit 5: Week 6 (\pm 2 days)	26
6.5.6	Visit 6: Week 8 (\pm 2 days)	26
6.5.7	Visit 7: Week 10 (\pm 2 days)	26
7	STATISTICAL PLAN	26
7.1	SAMPLE SIZE DETERMINATION	26
7.2	STATISTICAL METHODS	27
7.3	SUBJECT POPULATION(S) FOR ANALYSIS	27
8	SAFETY AND ADVERSE EVENTS	27
8.1	ADVERSE EVENT DEFINITIONS	27
8.2	CLASSIFICATION OF ADVERSE EVENTS BY SEVERITY	28
8.3	CLASSIFICATION OF ADVERSE EVENTS BY RELATIONSHIP TO STUDY TREATMENT	28
8.4	ACTION(S) TAKEN	29
8.5	OUTCOME	29
8.6	ADVERSE EVENT REPORTING	29
8.7	SERIOUS ADVERSE EVENT REPORTING	29
8.8	IN CASE OF AN EMERGENCY	30
8.9	DATA SAFETY MANAGEMENT PLAN	30
8.10	STUDY OVERSIGHT	30
9	CONFIDENTIALITY	31
10	SOURCE DOCUMENTS	31
10.1	RECORDS RETENTION	31
11	ETHICAL CONSIDERATIONS	31
12	STUDY FINANCES	32
12.1	FUNDING SOURCE	32
12.2	CONFLICT OF INTEREST	32
12.3	SUBJECT STIPENDS OR PAYMENTS	32
13	REFERENCES	33

SCHEDULE OF VISITS AND PROCEDURES

	Screening	Day 1 (Pre-Dose)	Day 1 (Post-Dose)	Week 2	Week 4	Week 6	Week 8	Week 10
Informed Consent	X							
Demographic Information	X							
Medical History/Con Meds	X							
Ophthalmic/Dry Eye History	X							
Vital Signs		X		X	X	X	X	X
Ophthalmic Examination (Slit lamp)	X	X		X	X	X	X	X
Ocular surface redness score	X	X		X	X	X	X	X
Schirmer 1 test and Rose Bengal staining	X						X	
Pregnancy Test (urine)*	X							
Best Spectacle Corrected Visual Acuity		X						X
Randomization visit		X						
First Study Medication		X						
Drug dispensation visits			X	X	X	X		
Instruction on study medication self-administration			X					
Ocular Surface Disease Index (OSDI)		X		X	X	X	X	X
Visual Analogue Scale (VAS)			X	X	X	X	X	
Physical inspection of nose & oropharynx				X	X	X	X	X
Clinical Global Impression (CGI)		X		X	X	X	X	X
Subject Global Assessment (SGI)		X		X	X	X	X	X
Adverse Events/ Concomitant Medications		X	X ⁺⁺	X	X	X	X	X

*If applicable ++ AEs only

ABBREVIATIONS

AE	Adverse Event
APC	Antigen-presenting cells
BSCVA	Best Spectacle Corrected Visual Acuity
EC	Ethics Committee
eDNA	Extracellular DNA
CNL	Corneal Neurobiology Laboratory
CRF	Case Report Form
CGI	Clinical Global Impression
DCF	Data Clarification Form
DED	Dry Eye Disease
DNase I	Deoxyribonuclease I
FDA	Food and Drug Administration
FVC	Forced vital capacity
GCP	Good Clinical Practice
ICH	International Conference on Harmonization
IB	Investigator's Brochure
IOP	Intraocular pressure
IRB	Institutional Review Board
KCS	Keratoconjunctivitis sicca

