3.2 Primary Study Endpoints

Primary Efficacy End Point: The primary end points after 8 weeks of treatment include the following: (1) the change in the Ocular Surface Disease Index (OSDI) which is a patient subjective rating scale; the Clinical Global Impression (CGI) of change in dry eye disease symptoms (physician's rating) and Subject Global Assessment (SGA) of overall change from baseline (patient's rating) will serve as anchors to OSDI, as has been described previously²⁹; (2) a mean reduction in ocular surface staining as measured by Rose Bengal dye staining and (3) the change in ocular surface redness score OR slit-lamp examination.

Primary Tolerability End Point: The change in the test substance tolerance between Day 1 (post-dose) and at weeks 2, 4, 6 and 8.

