4.4.2 Data Collection and Follow-up for Withdrawn Subjects

If a subject withdraws from the study prior to 8 weeks, the subject will be asked to complete the procedures outlined in the 10 week visit as well as the Test Substance Tolerance scale from 8 weeks, as soon as possible. Subjects who voluntarily withdraw from the study between 8 weeks and 10 weeks will be asked to complete procedures outlined in the 10 weeks visit as soon as possible. Subjects who are withdrawn due to adverse events will be followed at least until resolution or stabilization of the adverse event.

If the subject remains in the study for safety evaluation, follow-up visits will be scheduled according to the schedule of visits and procedures found in the synopsis.

5 Study Drug

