6.5.6 Visit 6: Week 8 (\pm 2 days)

Treatment Visit (after any dose for that day)

- Vital Signs
- Ophthalmic Examination (slit lamp examination, Ocular surface redness score, Rose Bengal staining, and a Schirmer 1 test)
- Physical Inspection of the Nose and Oropharynx
- OSDI
- Test Substance Tolerance
- Clinical Global Impression, Subject Global Assessment
- Review the subject's diary and record changes in concomitant medication, deviations from drug schedule and adverse events.

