6.5.7 Visit 7: Week 10 (\pm 2 days)

Follow-Up Visit

- Vital Signs
- Ophthalmic Examination (slit lamp examination, Ocular surface redness score)
- Physical Inspection of the Nose and Oropharynx
- BSCVA (Snellen)
- OSDI
- Clinical Global Impression, Subject Global Assessment
- Review the subject's diary and record changes in concomitant medication and adverse events.

7 Statistical Plan

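### The early-withdrawal visit omits Rose Bengal and Schirmer, so subjects rescued or stopped before Week 8 may have no post-baseline staining value although they stay in the analysis set

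*Combined protocol and SAP*

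**What the plan says.** - **Withdrawal rule.** Section 5.7 lists what may be done when a subject worsens or has an adverse event. If Restasis or a corticosteroid "is instituted and/or the study drug is discontinued, the subject will be withdrawn from the study". Section 5.6 has the same rule in other words: if such therapy is started during the study and/or the drug is "withdrawn, the subject will be excluded from the study".
- **Exit visit.** Under 4.4.2, for withdrawal before 8 weeks, "the subject will be asked to complete the procedures outlined in the 10 week visit as well as the Test Substance Tolerance scale".
- **What that visit contains.** The eye examination listed for Week 10 (6.5.7) is "Ophthalmic Examination (slit lamp examination, Ocular surface redness score" and nothing more. At Week 8 (6.5.6) it is "Ophthalmic Examination (slit lamp examination, Ocular surface redness score, Rose Bengal staining, and a Schirmer 1 test". In the Schedule of Visits, the row "Schirmer 1 test and Rose Bengal staining" is marked at Screening and Week 8 only.
- **A clause that may help.** Section 4.4.2 also says: "If the subject remains in the study for safety evaluation, follow-up visits will be scheduled according to the schedule of visits and procedures".
- **Endpoints.** Efficacy endpoint (2) in 3.2, after 8 weeks of treatment, is "a mean reduction in ocular surface staining as measured by Rose Bengal dye staining". Schirmer change and complete staining clearance are secondary endpoints 1 and 2 in 3.3.
- **Analysis set.** Sections 7.1 and 7.3 include anyone with two or more weeks of drops who attended Week 2. Neither removes a subject for later rescue or withdrawal.

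**The concern.** Sections 7.1 and 7.3 keep a subject who is rescued or stops drug after Week 2, yet the exit route collects neither of the two tests. Section 7.2 promises a 95% confidence interval for drug against placebo on the primary efficacy and secondary endpoints, and section 7 gives no missing-data method. An observed-data comparison of staining would then rest only on subjects who reached Week 8.

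Clinical worsening is one of the triggers for rescue, so the missing values would tend to belong to subjects doing badly. Stops for adverse events need not share that pattern. A difference between arms in how often or why subjects leave would carry into the staining, clearance and Schirmer comparisons, in either direction. A value that was never taken cannot be recovered by a later analysis rule.

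**Working it through.** **1. Post-baseline values for a subject who leaves between Week 2 and Week 8**

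| Measure | Scheduled on treatment | At exit visit | Post-baseline value if the exit route is followed |
|---|---|---|---|
| OSDI, redness | Weeks 2, 4, 6, 8 | Yes | Yes |
| Rose Bengal | Week 8 | No | None |
| Schirmer | Week 8 | No | None |

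The weekly follow-up after worsening in 5.6 names neither test. If the safety-evaluation clause in 4.4.2 keeps the subject on schedule to Week 8, the last two entries become one value each. Subjects who leave before the Week 2 visit are outside 7.3 and are not part of this point.

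**2. How many subjects**

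The documents give no rescue or stopping rate, and 5.6 expects no significant worsening, so the number may be 0. The only related figure is the 20% non-completion allowance in 7.1: 0.20 × 72 = 14.4 subjects. Assume that all of these leave before Week 8, that none is kept on schedule, and that a share s leaves after the Week 2 visit. The analysis set is then 72 − 14.4(1 − s), of whom 14.4s have no staining value:

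- s = 0: 0 of 57.6
- s = 0.5: 7.2 of 64.8 (11.1%)
- s = 1: 14.4 of 72 (20%)

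Per affected subject in an arm of 36, 1/36 = 2.8 percentage points of that arm's clearance proportion is undetermined. (An equal split is assumed; the unrestricted list in 5.3 does not guarantee it.)

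**3. Bias of an observed-only Week 8 comparison (illustration; every rate is assumed)**

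Take a standard normal outcome, higher being worse. The worst fraction q of a latent variable with correlation ρ to the outcome is rescued and lost. With z the 1 − q quantile, the observed mean is −ρφ(z)/(1 − q).

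- q = 0.20: −0.350ρ. q = 0.15: −0.274ρ. q = 0.10: −0.195ρ.
- 20% v 10%: 0.155ρ, which is 0.039 SD at ρ = 0.25 and 0.077 SD at ρ = 0.5.
- 15% v 10%: 0.079ρ, which is 0.020 SD and 0.040 SD.
- Equal q and equal ρ: 0.

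The standard error at 30 per arm is √(2/30) = 0.258 SD. The 20% v 10% bias is therefore 0.039/0.258 = 0.15 to 0.077/0.258 = 0.30 of a standard error.

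**4. What collecting the values does to that bias (20% v 10%)**

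Let a random fraction k = 0.8 of rescued subjects give a Week 8 value, improved by r SD through rescue. The observed mean becomes [−ρφ(z)(1 − k) − rkq]/(1 − q + kq). For ρ = 0.25 and r = 0.5:

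- 20% arm: (−0.0140 − 0.0800)/0.96 = −0.0979
- 10% arm: (−0.0088 − 0.0400)/0.98 = −0.0498
- Difference: −0.048

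If the pre-rescue exit value is used for all rescued subjects and differs from the unrescued Week 8 value by d on average, the bias is d × (0.20 − 0.10), or 0 to 0.05 SD for d from 0 to 0.5. If the target includes the effect of rescue, the true contrast at r = 0.5 is −0.5 × 0.10 = −0.05.

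| Target | ρ | No change | Week 8 kept, r = 0.5 | Week 8 kept, r = 1 | Exit value |
|---|---|---|---|---|---|
| No-rescue contrast | 0.25 | 0.039 | 0.048 | 0.091 | 0–0.05 |
| No-rescue contrast | 0.5 | 0.077 | 0.054 | 0.096 | 0–0.05 |
| Rescue included (r = 0.5) | 0.25 | 0.011 | 0.002 | – | – |
| Rescue included (r = 0.5) | 0.5 | 0.027 | 0.004 | – | – |

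Entries are absolute bias in SD.

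**The case against.** **The plan may already keep these subjects.** Section 4.4.1 follows withdrawn subjects for safety where possible, 4.4.2 follows adverse-event withdrawals to resolution or stabilisation, and 5.6 follows worsened subjects weekly. They are obvious candidates for the safety-evaluation clause, whose schedule includes both tests at Week 8. This stands in part: a reader might infer that rescued subjects are certain to lose their staining value, and the documents do not go that far. But the clause does not say whom it covers, and 5.6 and 5.7 call the same subjects excluded or withdrawn. Staff could apply it differently from one subject to the next.

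**Withdrawal on rescue is deliberate.** Section 5.6 withholds Restasis because benefit could not otherwise be attributed to rhDNase. That is a reason to end study treatment. It is no reason to skip staining before rescue starts.

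**The remedy may not reduce bias.** This stands. For a no-rescue contrast at correlation 0.25, keeping Week 8 values gives 0.048 to 0.091 SD and the exit value up to 0.05 SD, against 0.039 SD from doing nothing.

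**The reach is limited.** This stands. The synopsis names OSDI change as the primary efficacy measure, and 7.2 names a test for OSDI and none for staining. The primary safety endpoint (completing eight weeks of therapy) would also reveal unequal loss between arms, though it cannot supply the missing values.

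**Conclusion.** The gap is real and worth closing, but its likely numerical effect is small. If the exit route is followed, subjects in the 7.3 population who start Restasis or corticosteroids or stop drug before Week 8 have no post-baseline value for staining, staining clearance or Schirmer. Under assumed loss of 20% or 15% against 10% and correlations of 0.25 to 0.5, the bias is about 0.02 to 0.08 SD. It is 0 at equal rates and reasons, and its direction is unknown.

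Three stronger readings are not supported:

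- **That 14 of 72 is the most that could be affected.** The 20% in 7.1 is a planning allowance and not a limit on loss, and 8.1 allows subjects who withdraw for an adverse event to be replaced.
- **That the main efficacy result is compromised.** OSDI and redness have two-weekly and exit values.
- **That collecting the values removes the bias.** That depends on the target and on the unknown effect of rescue.

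Confidence is medium. The omission itself is plain in the text, but how the 4.4.2 clause would be applied and how many subjects would be affected are not.

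**What to change.** 1. In 4.4.2, 5.6 and 5.7, add Rose Bengal and Schirmer to the early-withdrawal visit, done when drug is stopped or before rescue starts where clinically possible.
2. State that rescue or stopping drug ends study treatment and not assessments, and that consenting subjects keep the Week 8 assessments. This settles whom the safety-evaluation clause covers.
3. In 5.6, for subjects already on study treatment, replace "withdrawn, the subject will be excluded from the study" with wording that matches 7.3.
4. In 7.2, report staining with the observed Week 8 value where there is one, and with the pre-rescue exit value as a sensitivity analysis.

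The rescue decision stays with the investigator.

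**Cost.** Wording in four sections, one extra pair of tests (both already used in the trial) for a few subjects, at a visit that already has a slit-lamp examination, and a few retained visits. Post-rescue Week 8 values partly reflect the rescue therapy, and exit values come earlier than the 8-week endpoint, so neither is a clean substitute. What is gained is that the analysed population has values to report.
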